4.5. Exploratory Endpoint Analyses

Unless otherwise specified, all exploratory efficacy analyses will be guided by the “efficacy” estimand and will be conducted using the EAS. Missing data will be handled using an MMRM.

The following efficacy analyses apply to both ISAs and will be carried out separately for each ISA.

Table GPIF.4.4. Exploratory Efficacy Analysis for Both ISAs

| Objective – Demonstrate Superiority of Tirzepatide MTD to Placebo for: | Endpoint | Analytical Approaches |
|--|---|---|
| Change in exploratory PROs | Change from baseline to Week 52 in: EQ-5D-5L utility index EQ-VAS scores | MMRM analysis described in Section 4.4.1.1 will be conducted. |
| | Percent of participants with improved categorical shift from baseline to Week 52 in: PGIC-OSA Sleepiness PGIC-OSA Fatigue PGIC-OSA Sleep quality PGIC-OSA Snoring | For each question, the proportion of participants with improvements from baseline will be summarized. Shift analysis from baseline to Week 52 will also be performed. |
| Change in parameters measured by Actigraphy (AX6) | Mean change from baseline to Week 52 in: Daytime sleep duration Daily step counts Average acceleration | MMRM analysis described in Section 4.4.1.1 will be conducted. |

Abbreviations: EQ-5D-5L = EuroQoL-5 Dimension-5 Level; EQ-VAS = EuroQol Visual Analogue Scale; ISA = intervention-specific appendix; MMRM = Mixed model repeated measures; MTD = maximum tolerated dose; PRO = patient-reported outcome; PGIC-OSA = Patient Global Impression of Change Obstructive Sleep Apnea.

The efficacy analyses summarized in [Table GPIF.4.5](#) only apply to participants in ISA1.

Table GPIF.4.5. Exploratory Efficacy Analysis Conducted only for ISA1 Participants

| Objective – Demonstrate Superiority of Tirzepatide MTD to placebo for: | Endpoint | Analytical Approaches |
|--|---|---|
| Change in parameters measured by WatchPAT300 | Change from baseline to Week 52 in PAT-based device determinations of: • pAHI • SASHB | MMRM analysis described in Section 4.4.1.1 will be conducted. |

Abbreviations: MMRM = mixed model repeated measures; MTD = maximum tolerated dose; pAHI = peripheral tone apnea-hypopnea index; PAT = peripheral arterial tonometry; SASHB = sleep apnea specific hypoxic burden.

4.6. Safety Analyses

Unless specified otherwise, safety assessments will be guided by the safety estimand. Thus, unless specified otherwise, safety analyses will be conducted in the safety analysis set ([Table GPIF.3.1](#)); all events that occur between the first dose date of study drug and the end date of study participation will be included, regardless of the adherence to study drug.

The statistical assessment of homogeneity of the distribution of categorical safety responses between tirzepatide MTD and placebo will be conducted using Fisher's exact test, unless specified otherwise.

The mean change from baseline differences among treatments at all scheduled visits will be assessed via an MMRM using REML. The model will include treatment group, stratification factors, visit and treatment-by-visit interaction as fixed effects, and baseline value of the safety parameter as a covariate. To model the covariance structure within participants, the unstructured covariance matrix will be used. If this model fails to converge, the covariance structures specified in [Section 4.3.1](#) will be tested in order until convergence is met. If the data does not warrant the MMRM model, then an ANCOVA model will be used.

For selected safety parameters, time-to-first-event analysis via the Cox-proportional hazards model may be conducted. Participants without the event will be censored at the end of study participation. For participants experiencing the event, the "time-to-first-event" will be the time (in days) from first dose to first occurrence of the event.

4.6.1. Analysis of Adverse Events

4.6.1.1. Treatment-Emergent Adverse Events

A TEAE is defined as an event that first occurred or worsened in severity after the first dose of study treatment. The MedDRA LLT will be used in the treatment-emergent derivation. The maximum severity for each LLT during the baseline period including ongoing medical history will be used as baseline severity. For events with a missing severity during the baseline period, it will be treated as "mild" in severity for determining treatment-emergence. Events with a missing severity during the postbaseline period will be treated as "severe" and treatment-emergence will be determined by comparing to baseline severity.

For events occurring on the day of taking study medication for the first time, the CRF-collected information (for example, if the event starts or worsens after the first dose) will be used to determine whether the event was pre- versus posttreatment if available. If the relevant information is not available, then the events will be counted as posttreatment.

Unless otherwise specified, the counts and percentages of participants with TEAEs will be summarized by treatment using MedDRA PT nested within SOC. Statistical comparisons will be applied at both the SOC and PT levels. Events will be ordered by decreasing frequency in the tirzepatide arm within the SOC. The SOC will be in alphabetical order.

An overview of the number and percentage of participants who experienced a TEAE, SAE, death, discontinued from study treatment or study due to an AE, or with a TEAE related to study treatment will be summarized by treatment.

The counts and percentages of participants with TEAEs by maximum severity will be summarized by treatment using the MedDRA PT within the SOC. For each participant and TEAE, the maximum severity for the MedDRA PT is the maximum postbaseline severity observed from all associated LLTs mapping to the MedDRA PT. The maximum severity will be determined based on the nonmissing severities. If all severities are missing for the defined postbaseline period of interest, it will show as missing in the table.

For events that are gender specific, the denominator and computation of the percentage will only include participants of the given gender.

4.6.1.2. Common Adverse Events

The counts and percentages of participants with TEAEs, overall and common (common TEAEs occurred in $\geq 5\%$ of participants before rounding), will be summarized by treatment using MedDRA PT. Events will be ordered by decreasing frequency in the tirzepatide arm.

4.6.1.3. Deaths

A listing of all deaths during the study will be provided. The listing will include participant identification including:

- treatment
- site number
- date of death
- age at the time of enrollment
- sex
- associated AE group identification
- time from last dose of study drug to death (if participant had discontinued study drug), and
- primary cause of death.

4.6.1.4. Other Serious Adverse Events

The counts and percentages of participants who experienced an SAE (including deaths and SAEs temporally associated or preceding deaths) during the postbaseline period will be summarized by treatment using MedDRA PT nested within SOC. Events will be ordered by decreasing frequency in the tirzepatide arm within the SOC. The SOC will be in alphabetical order.

A listing of all SAEs will be provided. The listing will include:

- treatment
- participant identification including the site number
- date of event
- age at the time of enrollment
- sex

- AE group identification
- MedDRA SOC and PT
- severity
- outcome
- relationship to study drug
- time from first dose of study drug to the event, and
- time from most recent dose to event (if participant discontinued study drug prior to the event).

4.6.1.5. Discontinuation Due to Adverse Events

The counts and percentages of participants who discontinued from study treatment or study due to an AE during the postbaseline period may be summarized by treatment group using MedDRA PT nested within SOC. Events will be ordered by decreasing frequency in the tirzepatide arm within the SOC.

4.6.2. Patient Narratives

Patient narratives will be provided for all participants who experience any of the following “notable” events:

- death
- SAE
- pregnancy, or
- permanent discontinuation of study treatment due to AEs.

Patient narratives (patient level data and summary paragraph) will be provided for participants in the randomized population with at least 1 notable event.

4.6.3. Special Safety Topics

For AESI or special safety topics, the counts and percentages of participants will be summarized by treatment and PT with decreasing frequency in the tirzepatide arm if the overall count is 10 or more. Individual participant level data may be presented. Displays with individual participant level data may be created using various formats, such as a customized listing and/or a customized graphical participant profile. AESI are defined in each section of special safety topics, where applicable.

4.6.3.1. Exocrine Pancreas Safety

4.6.3.1.1. Pancreatic Enzyme

Observed pancreatic enzyme data (p-amylase and lipase) will be summarized by treatment and nominal visit.

The counts and percentages of participants with maximum postbaseline pancreatic enzyme value exceeding the following thresholds will be provided by maximum baseline pancreatic enzyme value (\leq ULN, $>$ ULN), and postbaseline:

- $\leq 1 \times$ ULN
- (>1 to ≤ 3) \times ULN

- (>3 to ≤ 5) \times ULN
- (>5 to ≤ 10) \times ULN, and
- $>10 \times$ ULN.

An MMRM analysis will be used to analyze each pancreatic enzyme with a log-transformed (postbaseline measure/baseline measure) response variable and treatment, nominal visit, treatment-by-nominal visit interaction as fixed effects.

4.6.3.1.2. *Pancreatitis Events*

Summaries of adjudicated and investigator-reported pancreatic events will be provided by treatment. Detailed searching criteria can be found in Appendix 2 (Section 6.2).

Treatment-emergent adjudication-confirmed pancreatitis will be considered as an AESI. Listing of participants with adjudicated pancreatitis may be provided if deemed necessary.

4.6.3.2. *Gastrointestinal Adverse Events*

4.6.3.2.1. *Nausea, Vomiting, and Diarrhea*

Summaries and analyses for incidence and severity of nausea, vomiting (including “vomiting” and “vomiting projectile”), diarrhea (including “diarrhea” and “diarrhoea”), and 3 events combined, will be provided by each treatment group.

Summary of the prevalence over time for nausea, vomiting, and diarrhea will also be presented. Time to the onset of nausea, vomiting, and diarrhea will be plotted.

4.6.3.2.2. *Severe Gastrointestinal Events*

The PTs under the *Gastrointestinal disorders* SOC in MedDRA will be used to identify GI AEs, and only the PTs with serious/severe treatment-emergent cases will be considered as AESIs.

The counts and percentages of participants with severe/serious treatment-emergent GI events may be summarized by treatment, or a listing may be provided.

4.6.3.3. *Hepatobiliary Disorders*

4.6.3.3.1. *Hepatobiliary Events*

The counts and percentages of participants with treatment-emergent hepatic events may be summarized by treatment using the MedDRA PTs. The detailed search criteria can be found in Appendix 2 (Section 6.2).

Events related to acute gallbladder disease may also be summarized or a listing may be provided. The search criteria can be found in Appendix 2 (Section 6.2).

Severe/serious treatment-emergent hepatic events and acute gallbladder disease will be considered as AESIs.

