Statistical treatment comparisons will be performed between tirzepatide MTD and placebo. Unless otherwise noted, all tests of treatment effects will be conducted at a 2-sided alpha level of 0.05, and the confidence interval will be calculated at a 2-sided 95% level. In statistical summaries and analyses, participants will be analyzed as randomized. Analysis models will use geographic region (US/OUS) as a covariate when applicable.

Analysis of covariance will be used to analyze continuous variables collected only at baseline and endpoint. Unless otherwise specified, the model will include treatment and strata (geographic region [US/OUS], AHI stratum [not severe (AHI <30), severe (AHI \geq 30)], and gender) as fixed effects and baseline as a covariate.

MMRMs will be used to analyze continuous variables collected at baseline and more than 1 postbaseline visit. For the MMRM analysis, REML will be used to obtain model parameter estimates for continuous longitudinal variables. All the longitudinal observations at each scheduled postbaseline visit will be included in the analysis. The model will include the fixed class effects of treatment, strata (geographic region [US/OUS] and gender), visit, and treatment-by-visit interaction, as well as the continuous, fixed covariate of baseline value. For analyses of variables other than AHI, the AHI stratum will also be included in the model. Significance tests will be based on least squares means and Type III tests.

For continuous measures, summary statistics may include sample size, mean, standard deviation, median, minimum, and maximum for both the actual and the change from baseline measurements. Least-square means and standard errors derived from the analysis models will also be displayed for the change from baseline measurements. Treatment comparisons will be displayed showing the treatment difference least-square means and the 95% confidence intervals for the treatment differences, along with the p-values for the treatment comparisons.

For categorical measures, summary statistics may include sample size, frequency, and percentages. Fisher's exact test or Pearson's chi-square test will be used for treatment comparisons unless otherwise specified.

Not all analyses described in this SAP will necessarily be included in the CSRs. Any analysis described in this SAP and not provided in the CSR would be available upon request.

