4.1.1. Adjustment for Covariates

The study is stratified by country/geographic region, OSA severity (not severe [AHI <30], severe [AHI \geq 30]), and gender. Unless otherwise specified, the following factors will be adjusted for: geographic region (US/OUS), OSA severity (not severe [AHI <30], severe [AHI \geq 30]), and gender. The value for stratification factors will be obtained from the data collected or derived from the eCRF or PSG results. In addition, the baseline value of the endpoint will be used as a covariate when appropriate.

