4.6.3.10. Renal Safety

Laboratory measures related to renal safety will be analyzed as specified for laboratory measurements in Section 4.6.5.

In addition, 2 shift tables examining renal function will be created. A minimum-to-minimum shift table of estimated glomerular filtration rate estimated by the Chronic Kidney Disease Epidemiology Collaboration equation with units mL/min/1.73 m², using categories (<30, ≥30 to <45, ≥45 to <60, ≥60 to <90, and ≥90 mL/min/1.73 m²). A maximum-to-maximum shift table of UACR, using the categories UACR <30 mg/g, ≥30 mg/g UACR to ≤300 mg/g, UACR >300 mg/g (respectively, these represent normal, microalbuminuria, and macroalbuminuria).

MMRM analyses as described in Section 4.6 for estimated glomerular filtration rate and log-transformed UACR will be provided. Log transformation will be performed for UACR.

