4.6.5. Clinical Laboratory Evaluation

Limits from the performing laboratory will be used to define low (L) and high (H). Descriptive summaries by treatment and by nominal visit will be provided for the baseline and postbaseline values as well as the change from baseline values. The associated descriptive will be presented in International System of Units and in conventional units.

For selected laboratory analyte measurements collected quantitatively, observed, and change from baseline values for each visit may be displayed in plots for participants who have both a baseline and at least 1 postbaseline planned measurement. Unplanned postbaseline measurements will be excluded from plots.

A shift table will be provided including unplanned measurements. The shift table will include the number and percentage of participants within each baseline category (low, normal, high, or missing) versus each postbaseline category (low, normal, high, or missing) by treatment. The proportion of participants shifted will be compared between treatments using Fisher's exact test.

For qualitative laboratory analytes, the number and percentage of participants with normal and abnormal values will be summarized by treatment.

A listing of abnormal findings will be created for laboratory analyte measurements, including qualitative measures. The listing will include:

- participant identification
- treatment group
- laboratory collection date
- study day
- analyte name, and
- analyte finding.

The MMRM model or ANCOVA (if MMRM model is not applicable) as described in Section 4.6 will be used for the analysis during the treatment period (excluding the safety follow-up period) for the continuous measurements for selected laboratory tests with or without log-transformed (postbaseline measure/baseline measure) response variables. For measures analyzed using log-transformed values, the results will be presented with the scale back transforming to the original, related scale.

The summary of treatment-emergent abnormal, high, or low laboratory results any time will be provided.

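### The pancreatic-enzyme MMRM in SAP 4.6.3.1.1 lists no baseline covariate or stratification factors, unlike the SAP's general safety model; the comparison is valid but usually somewhat less precise

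*SAP*

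**What the plan says.** **The pancreatic section.** SAP 4.6.3.1.1 states: "An MMRM analysis will be used to analyze each pancreatic enzyme with a log-transformed (postbaseline measure/baseline measure". The sentence goes on to name the "response variable and treatment, nominal visit, treatment-by-nominal visit interaction as fixed effects". It mentions neither a baseline covariate nor the stratification factors, and it does not point to another section for the rest of the model.

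**The general safety model.** SAP 4.6 defines the MMRM for mean change from baseline with treatment group, stratification factors, "visit and treatment-by-visit interaction as fixed effects, and baseline value of the safety parameter as a covariate".

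**Where the general model is applied.** SAP 4.6.5 uses the Section 4.6 model "for the continuous measurements for selected laboratory tests with or without log-transformed (postbaseline measure/baseline measure) response variables". SAP 4.6.3.10 does the same for renal measures: "MMRM analyses as described in Section 4.6 for estimated glomerular filtration rate and log-transformed UACR will be provided". The liver-enzyme section (SAP 4.6.3.3.2) refers to 4.6.5.

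**The general covariate rule.** SAP 4.1.1 adjusts by default for region (US/OUS), OSA severity and gender, and adds that "the baseline value of the endpoint will be used as a covariate when appropriate".

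**The concern.** Two specifications in one SAP differ for the same kind of response, and no reason is given. A programmer who follows 4.6.3.1.1 literally would fit an unadjusted change score on the log scale.

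It is easy to assume that a ratio to baseline already accounts for baseline. It does so only by fixing the regression slope of log postbaseline on log baseline at 1 instead of estimating it. If the true slope is below 1, an arm that happens to start higher will tend to show a smaller rise, and the variance is larger than it need be.

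At stake is the precision of the between-arm enzyme comparison, and clarity about which model will be run for a prespecified special safety topic.

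**Working it through.** The plan states no power, precision or expected difference for the enzyme MMRM, so there is no figure of its own to reproduce.

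**Inputs**
- Response and terms: SAP 4.6.3.1.1 and 4.6, as above.
- About 103 per arm per ISA (SAP Section 5). The variance ratios below do not depend on this number.
- Two-sided 0.05 (SAP 4.1: "all tests of treatment effects will be conducted at a 2-sided alpha level of 0.05").
- Correlation ρ between log baseline and log postbaseline enzyme: **not in the documents**; assumed 0.5 to 0.9.
- Baseline SD s0 and postbaseline SD s1 on the log scale: **not in the documents**; first taken as equal, then varied.

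**Formulas, at one visit**
- Unadjusted log ratio: variance = s0² + s1² − 2ρ·s0·s1
- Baseline-adjusted: variance = s1²(1 − ρ²)
- Difference = (s0 − ρ·s1)². This is never negative, and it is zero only when the slope ρ·s1/s0 equals 1.
- The unadjusted estimate carries (ρ·s1/s0 − 1) times the realised baseline difference.

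**Equal SDs.** The variances become 2s²(1 − ρ) and s²(1 − ρ²), with ratio 2/(1 + ρ). At ρ = 0.5 they are 1.00s² and 0.75s²; at ρ = 0.9, 0.20s² and 0.19s². Adjusted interval width relative to unadjusted is √((1 + ρ)/2). The equivalent sample size is 103(1 + ρ)/2.

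| ρ (assumed) | Variance, unadjusted/adjusted | CI narrowing with adjustment | 103 per arm unadjusted is worth, adjusted | Share of baseline difference carried (opposite sign) | Power unadjusted where adjusted has 90% |
|---|---|---|---|---|---|
| 0.5 | 1.33 | 13.4% | 77 | 50% | 80.2% |
| 0.6 | 1.25 | 10.6% | 82 | 40% | 82.6% |
| 0.7 | 1.18 | 7.8% | 88 | 30% | 84.8% |
| 0.8 | 1.11 | 5.1% | 93 | 20% | 86.8% |
| 0.9 | 1.05 | 2.5% | 98 | 10% | 88.5% |

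**Unequal SDs**
- s1/s0 = 0.8, ρ = 0.5: unadjusted 1 + 0.64 − 0.80 = 0.84; adjusted 0.64 × 0.75 = 0.48; ratio 1.75 (slope 0.40).
- s1/s0 = 1.5, ρ = 0.7: unadjusted 1 + 2.25 − 2.10 = 1.15; adjusted 2.25 × 0.51 = 1.1475; ratio 1.002 (slope 1.05).

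So the loss can exceed the table or vanish, depending on how close the slope is to 1.

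**Size of the chance imbalance.** Its SD at 103 per arm is √(2/103) = 0.14 baseline SDs, with a 95% range of about ±0.27. With equal SDs the amount carried is typically 0.50 × 0.14 = 0.07 SD at ρ = 0.5 and 0.30 × 0.14 = 0.04 SD at ρ = 0.7. At the 95% limit it is about 0.14 and 0.08 SD.

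**Simulation check.** In 20,000 trials with 103 per arm, three postbaseline visits, equal SDs and no treatment effect, the variance ratios were 1.33 (ρ = 0.5) and 1.18 (ρ = 0.7). The slope of the estimate on baseline imbalance was −0.50 and −0.31 unadjusted, and 0.00 and −0.01 adjusted. Both estimators averaged about 0.

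The effect of leaving out the stratification factors was not quantified; the documents give nothing on how strongly they predict enzyme levels.

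**The case against.** **The sentence may be shorthand.** It lists fixed effects and nowhere says that baseline is excluded. Section 4.6 itself names baseline separately, as a covariate. The default rule in 4.1.1 and the laboratory model in 4.6.5 could be taken to cover amylase and lipase. This reading is possible, and nothing shows a deliberate decision to drop baseline. But the stratification factors, which 4.6 lists before visit and its interaction as fixed effects, are missing too, and the renal and liver sections make their cross-references explicit where this one does not. As written, the list reads as complete.

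**A reader might infer that the comparison is biased, or that it could mask or exaggerate an enzyme signal.** The documents do not support that. Regression to the mean acts on both arms under randomisation, and the estimate is unbiased on average. The imbalance matters only conditionally on the baseline difference that occurs. Nor is it a second defect on top of the imprecision: with equal SDs, 2s²(1 − ρ) = s²(1 − ρ²) + s²(1 − ρ)², and the last term is the carried imbalance, already inside the unadjusted standard error.

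**A reader might also infer that adjustment gains at every correlation below 1.** That needs equal SDs. In general the gain vanishes when ρ·s1/s0 = 1, for example at ρ = 0.7 with an SD ratio of about 1.43 (1/0.7).

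**Little depends on this one model.** SAP 2.1 generally leaves safety assessments outside the multiplicity adjustment. The same pancreatic section tabulates maximum postbaseline enzyme categories by baseline category, and pancreatitis is adjudicated by a blinded committee (Protocol 10.1.5.2). This stands, and it limits the weight of the point.

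**Conclusion.** The point holds as a minor one. SAP 4.6.3.1.1 specifies a reduced model, without explanation, for a response that SAP 4.6.5 analyses with baseline and stratification factors. The reduced analysis is valid, but less precise unless the log-scale slope is 1. With equal SDs and ρ of 0.5 to 0.9, adjustment would narrow intervals by about 13% down to 3%; for ρ of 0.8 to 0.9 the gain is only about 5% to 3%. Both the correlation and the SD ratio are assumptions, and other SD ratios move the gain in either direction. No primary or key secondary inference is touched.

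**What to change.** In SAP 4.6.3.1.1, state that the Section 4.6 MMRM applies to log(postbaseline/baseline), with log baseline enzyme as covariate and the stratification factors as fixed effects. If the reduced model is intended, say so and give the reason.

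The cost is one sentence in the SAP and the matching line of code. Both enzymes are already scheduled at Visit 1 and at Weeks 12, 24 and 52 (Protocol 1.3), so no new data are needed. The wording should be settled before the first ISA is unblinded, which is when the SAP says it will be final.
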